[figure not shown]

## SYNOPSIS

Name of Sponsor Company: Aldeyra Therapeutics, Inc.	Investigational Product: ADX-2191	
Title of Protocol: A multicenter, adaptive Phase 3 clinical trial of repeated intravitreal injections of ADX-2191 versus standard-of-care for the prevention of proliferative vitreoretinopathy		
Protocol Number: ADX-2191-PVR-001	Phase: 3	Indication: Prevention of Proliferative vitreoretinopathy
Subject Population: Adult subjects undergoing pars plana vitrectomy for the following indications: 

• Recurrent retinal detachment due to proliferative vitreoretinopathy (PVR) with documented starfolds in at least three cumulative clock hours on retinal imaging.

• Retinal detachment associated with open globe injury (OGI).

		
Number of Subjects: The trial will utilize an adaptive design with the number of subjects enrolled for Part 2 determined in Part 1. Part 1: Approximately 100-120 subjects will be enrolled to obtain approximately 100 evaluable eyes (50 subjects per treatment). Part 2: An additional 100-360 subjects will be enrolled to obtain approximately 100-300 evaluable eyes (50-150 subjects per treatment); to be statistically powered following completion of Part 1.		
Number of Centers: Approximately up to 30 sites in the United States		
Test Products / Dose / Mode of Administration: ADX-2191 (intravitreal methotrexate 0.8%) 400 mcg in 0.05 mL for 13 repeated intravitreal injections over 16 weeks		
Overall Design: In Part 1a of the GUARD Study (prior to activation of Protocol Version 5.0, dated May 5 2021), eligible subjects will be randomized 1:1 intraoperatively to either the Control or Intervention cohort. Subjects in the Control cohort will receive Standard Procedures only. In Part 1b of the GUARD Study (after activation of Protocol Version 5.0, dated May 5 2021), eligible subjects will no longer be randomized and all enrolled subjects will be placed in the Intervention Cohort. Subjects in the Intervention cohort will receive Standard Procedures and intravitreal ADX-2191 injections (Figure 1). In Part 1a, stratification will be used to balance treatment assignments within key subgroups. Subjects are to be stratified by clinical presentation (recurrent retinal detachment vs. OGI) and number of recurrent retinal detachments (>3 vs. ≤3). Subjects enrolled in Part 1 will not be eligible to participate in Part 2 nor will they be eligible to be randomized again during Part 1. Clinical trial procedures to be conducted in Part 1 and Part 2 are outlined in the Schedule of Assessments (Table 1).		

**Primary Objective:**

To evaluate the safety and efficacy of repeated intravitreal ADX-2191 injections as a pharmacologic approach to prevent PVR secondary to recurrent retinal detachment and OGI.

**Secondary Objective (Part 1 only):**

Part 1 will confirm the sample size to be utilized in Part 2.

**Primary Endpoint:**

The primary endpoint in Part 1 and Part 2 is the rate of recurrent retinal detachment requiring reoperation within 24 weeks from time of enrollment in drug-treated subjects compared to historical rates of retinal detachment for Grade C PVR. An evaluating investigator should determine whether the primary endpoint has been met. The primary endpoint requires verification by the Central Reading Center (CRC) before recurrent retinal detachment reoperation. In cases where CRC verification is not possible due to technical limitations with the Optical Coherence Tomography or fundus photograph, then the evaluating investigator will contact the trial medical monitor to confirm whether the primary endpoint has been met.

Recurrent retinal detachment is defined as either one, or, both of the following:

1. Spectral-Domain Optical Coherence Tomography (SD-OCT) demonstrating fovea-off retinal detachment (subfoveal fluid that is contiguous with a peripheral detachment);
2. Color fundus photographic documentation of a rhegmatogenous or tractional (or undetermined) retinal detachment that has progressed posterior to the Mandatory Reoperation Zone, as defined by a circle centered on the fovea, with a radius halfway between the arcades and the equator (Figure 2).

Stable, peripheral rhegmatogenous or tractional (or undetermined) detachments anterior to the mid-periphery may be observed or demarcated with laser at the Investigator's discretion and will not be counted as a failure.

Subjects who have retinal detachment within 1-week post-operatively will be deemed to have failed Day 0 (day of surgery) and will be removed from the efficacy analysis. Retinal detachment is defined as subjects who meet either of the recurrent retinal detachment imaging criteria as defined in the Primary Endpoint.

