### **2.2. Clinical Trial Endpoints**

#### **2.2.1. Primary Endpoints**

The primary endpoint in Part 1 and Part 2 is recurrent retinal detachment requiring reoperation within 24 weeks from time of enrollment. An evaluating investigator should determine whether the primary endpoint has been met. The primary endpoint requires verification by the Central Reading Center (CRC) before recurrent retinal detachment reoperation. In cases where CRC verification is not possible due to technical limitations with the Optical Coherence Tomography or fundus photograph, then the evaluating investigator will contact the trial medical monitor to confirm whether the primary endpoint has been met. These verification processes provide an additional level of objectivity in end point evaluation.

Definition of recurrent retinal detachment (defined as either one OR both of the following):

1. Spectral-Domain Optical Coherence Tomography (SD-OCT) demonstrating fovea-off retinal detachment (subfoveal fluid that is contiguous with a peripheral detachment);
2. Color fundus photographic documentation of a rhegmatogenous or tractional (or undetermined) retinal detachment that has progressed posterior to the Mandatory Reoperation Zone, as defined as defined by a circle centered on the fovea, with a radius halfway between the arcades and the equator (Figure 2).

Stable, peripheral rhegmatogenous or tractional (or undetermined) detachments anterior to the mid-periphery may be observed or demarcated with laser at the investigator's discretion and will not be counted as failure.

Subjects who have retinal detachment within 1-week post-operatively will be deemed to have failed Day 0 (day of surgery) and will be removed from the efficacy analysis. These will be considered "dropped" subjects. Subjects receiving investigational product during this period will continue to be followed for safety. Retinal detachment is defined as subjects who meet either of the recurrent retinal detachment imaging criteria as defined in the Primary Endpoint.

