## **9.4. Statistical Analysis**

### **9.4.1. General Considerations**

Prior to database lock, the Sponsor will finalize a statistical analysis plan (SAP) detailing all planned analyses. Any analyses conducted in addition to those specified in the SAP will be clearly documented as post hoc. A summary of the currently planned analyses for the primary and secondary outcome variables is found below.

Quantitative variables will be summarized descriptively using number of subjects (n), mean, standard deviation, median, minimum, and maximum. Qualitative variables will be summarized using counts and percentages.

All summaries will be presented by treatment group. Summaries will be provided for demographics, baseline medical history, concurrent therapies, and subject disposition.

For the purpose of summarization, medical history, concurrent therapies, and adverse events will be coded to MedDRA and WHO Drug dictionaries, as appropriate.

All analyses will be two-sided at a significance level of 0.05. The 95% confidence intervals will be provided where appropriate.

The primary endpoint analysis will compare retinal detachment rates of drug-treated subjects to a historical control rate, which will be a weighted average of the retinal re-detachment rates from two prior Grade C PVR prospective clinical trials with similar inclusion criteria (Banerjee, 2017; Schiff, 2007).

The SAP will serve as the final determinant of the statistical procedures, notwithstanding language herein.

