#### **9.4.5. Primary Efficacy Analyses**

The primary efficacy variable of recurrent of retinal detachments (defined in Section 3.6) due to PVR requiring re-operation within six months from enrollment will be measured as binary variable (indicating recurrent of detachment or not). Briefly, a 95% confidence interval around the proportion of retinal detachment in drug-treated subjects will be generated, and the primary endpoint will have been deemed to have been met if the upper bound of the confidence interval is lower than the weighted average historical control detachment rate. The primary efficacy analyses will be conducted on the ITT population with observed data only. Subjects who discontinue investigational treatment early will be encouraged to stay for any remaining safety assessments until the conclusion of the clinical trial. Subjects who have retinal detachment within 1-week post-operatively will be deemed to have failed Day 0 (day of surgery), and will be removed from the efficacy analysis.

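### The primary success rule sets a restricted drug-arm event against a historical re-detachment rate that is not required to count the same event

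*Combined protocol and SAP*

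**What the plan says.** **Drug side.** The Synopsis gives the primary endpoint as the "rate of recurrent retinal detachment requiring reoperation within 24 weeks from time of enrollment". It and Section 2.2.1 define recurrent detachment by either of two imaging findings: fovea-off on SD-OCT, or, on fundus photographs, a "retinal detachment that has progressed posterior to the Mandatory Reoperation Zone". Stable peripheral detachments "may be observed or demarcated with laser at the Investigator's discretion and will not be counted as a failure". Eyes that detach within a week of surgery leave the efficacy analysis (Synopsis, Sections 2.2.1, 4.3, 9.1.1 and 9.4.5). Section 9.4.5 adds that the event must be due to PVR.

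**Historical side.** The Synopsis compares the rate "in drug-treated subjects compared to historical rates of retinal detachment for Grade C PVR". Section 9.4.1 describes the control rate, "which will be a weighted average of the retinal re-detachment rates from two prior Grade C PVR prospective clinical trials", and says those trials had similar inclusion criteria. It gives no rate, weight, event definition or rule for early failures.

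**Decision rule.** Under Section 9.4.5 the endpoint is met "if the upper bound of the confidence interval is lower than the weighted average historical control detachment rate". Section 9.4.3 says that only one hypothesis is tested. Section 9.2 states that hypothesis as recurrent detachment due to PVR, on ADX-2191 and in the historical control, over 24 weeks.

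**The concern.** A one-sample test against a fixed number has no concurrent arm to absorb a difference in what was counted. Suppose the two earlier trials counted some re-detachments that this protocol would not: peripheral ones that were watched or lasered, ones never reoperated, ones in the first week, or ones not due to PVR. An ineffective drug would then have an expected rate below the threshold through definition alone, and the rule would read the gap as benefit.

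Similar inclusion criteria do not deal with this, because they describe who was enrolled and not what was counted. At stake is the false-success rate of the only test that decides the trial. The lower tail of a two-sided 95% interval should hold it at 2.5%.

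**Working it through.** **1. The plan's own figure.** Section 9.3.1 gives about 80% power for the initial two-arm design: rates 0.2 and 0.5, 45 per group, two-sided 0.05.

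- Uncorrected: n = [1.96·√(2·0.35·0.65) + 0.8416·√(0.2·0.8 + 0.5·0.5)]² / 0.3² = 1.861² / 0.09 = 38.5, so 39 per group.
- Continuity-corrected: (38.48/4)·[1 + √(1 + 4/(38.48·0.3))]² = 44.9, so 45 per group.

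The figure reproduces with the correction (power 80.1% at 45 per group). It belongs to the randomized comparison. The documents give no power or error calculation for the single-arm rule.

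**2. The two sides compared.**

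| Feature | Drug-arm event | Historical rate |
|---|---|---|
| Location | Fovea-off or behind the zone | Not stated |
| Reoperation | Required | Not stated |
| Stable peripheral detachment | Not a failure | Not stated |
| First-week detachment | Eye removed | Not stated |
| Cause | Due to PVR (9.2, 9.4.5) | Due to PVR in the hypothesis (9.2); not in the derivation (9.4.1) |
| Time | 24 weeks (six months in 9.4.5) | 24 weeks in the hypothesis (9.2); not in the derivation (9.4.1) |

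Section 9.2 presupposes a common event. Sections 9.4.1 and 9.4.5, which produce the number, do nothing to secure it.

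**3. Sensitivity of the rule.** These inputs are assumptions:

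- Threshold T: 0.20 to 0.55. The documents give no threshold. The ends are 1 − 0.80 and 1 − 0.45, from the background anatomic success of 45% to 80% in Section 1.1.
- Drug-treated eyes n: 70 or 100. Section 9.3.1 plans about 100 evaluable eyes, and Part 1a also enrolled controls.
- f: the share of historical events that would not meet this protocol's definition. It is unknown; 0, 10% and 20% are shown.
- Interval: exact (Clopper-Pearson). The plan names no method.

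Let c be the largest event count whose upper 95% bound lies below T. For an ineffective drug the expected rate is T(1 − f), and the chance of success is P(X ≤ c) with X binomial(n, T(1 − f)). Example: n = 100 and T = 0.50. An observed 39/100 has upper bound 0.493 and 40/100 has 0.503, so c = 39. With f = 10% the true rate is 0.45 and P(X ≤ 39) = 13.4%.

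| T | n | c | f = 0 | f = 10% | f = 20% |
|---|---|---|---|---|---|
| 0.20 | 70 | 7 | 2.0% | 4.9% | 11.0% |
| 0.20 | 100 | 11 | 1.3% | 3.9% | 10.6% |
| 0.35 | 70 | 16 | 2.0% | 7.4% | 20.6% |
| 0.35 | 100 | 25 | 2.1% | 9.6% | 29.3% |
| 0.40 | 100 | 30 | 2.5% | 12.5% | 37.8% |
| 0.50 | 70 | 26 | 2.1% | 11.4% | 36.0% |
| 0.50 | 100 | 39 | 1.8% | 13.4% | 46.2% |
| 0.55 | 70 | 29 | 1.6% | 10.9% | 37.9% |
| 0.55 | 100 | 44 | 1.8% | 15.9% | 54.2% |

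Counts are whole numbers, so sizes between 70 and 100 move in a saw-tooth and can fall slightly outside these ranges. A Wilson interval at n = 100 and T = 0.50 allows 40 events and gives 2.8%, 18.3% and 54.3%.

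**4. First-week removals.** These leave both numerator and denominator, so they are not quite f. If a share g of eyes detaches in week one and history counted them, the drug-arm rate becomes (T − g)/(1 − g). That equals an f of g(1 − T)/[T(1 − g)]. For an assumed g of 5% and T = 0.50, f = 0.025/0.475 = 5.3%.

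**The case against.** The strongest reply is that the documents never describe the historical rate as counting every re-detachment. The cited trials' definitions cannot be seen here and may be broader, equal or narrower. Bare wording proves little, because Sections 9.4.1 and 9.4.5 use the same shorthand for the drug arm, where the event is plainly restricted. Section 9.2 writes one event and one 24-week window for both sides. All of this stands. A reader might infer that the threshold is a rate of any re-detachment, or that ADX-2191 can win by definition; both would be inferences from silence. Nor can it be said that the historical side has no time limit, given Section 9.2. Retained silicone oil comes from the eligibility and surgical rules, not from the endpoint definition.

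It is also fair that f has no basis in the documents and drives the result, and that a low threshold softens it.

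Two mitigations exist. The secondary logistic regression compares drug with standard of care inside the trial, and total retinal attachment at Week 24 would reveal peripheral detachments. Neither enters the success rule, and the second is exploratory and descriptive only. Section 9.4.1 defers final procedures to an SAP, but nothing in the documents supplied settles the historical event.

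The objection removes the claim of a proven mismatch. It does not supply the missing link between the hypothesis in Section 9.2 and the number used in Section 9.4.5.

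**Conclusion.** The concern holds as a gap in the sole success criterion: the plan neither shows nor requires that both sides count the same event and handle early failures alike. This is more than missing detail, because inserting the published re-detachment rates as Section 9.4.1 is written could yield a false success.

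Direction: if the historical event is broader, the bias favours ADX-2191; if it is narrower, the bias goes the other way. Size, under the stated assumptions at 70 or 100 eyes: false success of 1.3% to 2.5% with matched events, about 4% to 16% when 10% of historical events would not qualify, and about 11% to 54% when 20% would not. These figures show sensitivity. They are not an estimate of inflation in this trial.

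**What to change.** Amend Sections 9.4.1 and 9.4.5, and carry the text into the SAP, before database lock:

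1. Derive the threshold from historical events matched to the Section 2.2.1 event as closely as the two trials' reports allow: severity, reoperation, 24 weeks, first-week exclusion and PVR as cause.
2. State each trial's event definition, time point, early-failure handling, rate and weight, the resulting threshold, and any mismatch that remains.
3. Where matching is not possible, add a pre-specified supportive analysis that scores the drug arm on the historical trials' own definition. That could be any re-detachment, with first-week cases counted if they were counted there. Use the fundus photographs and SD-OCT already scheduled. State that the efficacy conclusion will be limited if the two analyses disagree.
4. Correct the cross-reference in Section 9.4.5, which sends the reader to Section 3.6 for a definition that stands in Section 2.2.1.

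The primary endpoint need not be replaced. The cost is protocol and SAP wording, work on the historical reports and one further analysis, with no new visits. The threshold may fall, or the drug-arm rate in the supportive analysis may rise, and either makes success harder to claim. Full matching may prove impossible if the reports lack event-level detail, which is why the third step is needed.

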**Secondary Endpoints:**

- Comparison of retinal detachment rates across standard of care and drug-treated subjects.
- Best-corrected Visual Acuity (BCVA) change from Screening (Visit 1) level to Week 24 (as measured using an Early Treatment Diabetic Retinopathy Study [ETDRS] chart by masked technicians).

**Exploratory Endpoints:**

Exploratory endpoints in Part 1 and Part 2 include:

- Total number of vitrectomy surgeries performed by Week 24
- Total retinal attachment at Week 24
- Total macular attachment at Week 24
- Central macular subfield thickness (as measured by SD-OCT) at Week 24
- Macular epiretinal membrane (as visualized by SD-OCT) at Week 24
- Macular and extramacular epiretinal membrane visible on color fundus photographs at Week 24
- Percentage of eyes with intraocular pressure (IOP) < 5 mmHg at Week 24

**Safety Evaluations:**

Safety endpoints in Part 1 and Part 2 include:

- BCVA at distance utilizing an ETDRS chart
- IOP
- Slit-lamp examination
- Dilated ophthalmoscopy
- Adverse event (AE) query (reported, elicited, and observed)

**Criteria for Inclusion:**

Subjects meeting ALL of the following criteria will be considered eligible for clinical trial entry:

1. Subject is 18 years or older of any gender or any race.
2. Subjects are undergoing pars plana vitrectomy for the following indications:
  - a. Recurrent retinal detachment due to proliferative vitreoretinopathy (PVR) with documented starfolds in at least three cumulative clock hours on retinal imaging.
  - b. Retinal detachment associated with open globe injury (OGI).
3. Subjects must undergo silicone oil tamponade as part of the pars plana vitrectomy.
4. Investigators must agree to follow surgical principles as outlined in Section 6.9
5. At the conclusion of the retinal detachment surgical repair, the retina must be completely reattached, and, in the surgeon's best judgment, the subject should have a high likelihood of benefitting from enrollment in the clinical trial.
6. Subject is willing and able to provide written informed consent, comply with clinical trial procedures, and return for all clinical trial visits.
7. Subjects of childbearing potential, both male and female, must agree to use two forms of birth control for the duration of the clinical trial. Males should continue to use the two forms of birth control for a minimum of three months after last injection (30 days after completion of Visit 16/Week 24). Females of childbearing potential must use the two forms of birth control for a minimum of 30 days following their last injection.
8. For females of child-bearing potential, subjects must have a negative pregnancy test at Screening and not lactating.

**Criteria for Exclusion:**

Subjects meeting ANY of the following criteria in the study eye will be excluded from the clinical trial:

1. No Light Perception vision at screening exam.
2. Pre-phthisis eyes as per Investigator's assessment.
3. History of severe non-proliferative or proliferative diabetic retinopathy.
4. History of significant intraocular inflammatory disease requiring the use of systemic anti-inflammatory medication or an intraocular anti-inflammatory medication.
5. History of severe dry eye or other significant corneal disease.
6. History of incisional glaucoma surgery or ciliary body destructive procedures.

7. Other planned eye surgery during the course of the trial (including subjects with a diagnosis of bilateral detachments).
8. Participation in a clinical trial with an investigational medicinal product or investigational device within 90 days of subject enrollment.
9. Any clinically significant laboratory test abnormalities or a history of any other systemic or ophthalmic condition or circumstances which, in the opinion of the Investigator, could compromise the subject's ability to comply with the protocol or that could compromise the subject's safety or the interpretation of the clinical trial results.
10. History of more than 6 retinal detachments.
11. Hypersensitivity to Methotrexate medication.
12. Have previously received Methotrexate intravitreally at any time or plan to receive intravitreal methotrexate during the study period, or received systemic Methotrexate administration within 3 months of Screening visit.
13. Patients who might need to use Methotrexate for other medical conditions during the study period.

[figure not shown]
**Summary of Known and Potential Risks and Benefits to Human Subjects**

Refer to the Investigator's Brochure

[figure not shown]
**Data Safety Monitoring Board:**

Masked safety data will be reviewed throughout the clinical trial by Aldeyra. An external Data Safety and Monitoring Board (DSMB) will review selected unmasked data for safety assessment. The review frequency, criteria, and the process for making recommendations will be defined in the DSMB charter.

**Figure 1: Clinical Trial (Part 1 and Part 2) Flow Diagram**

Note: The initial ADX-2191 intravitreal injection may be performed Day 0 (intra-operatively) or Day One (post-operatively). As of Protocol Version 5.0 (dated May 5 2021), eligible subjects will no longer be randomized and all enrolled subjects will be placed in the Intervention Cohort.

Pre-Injection Assessment By Treating Investigator 				X	X	X	X	X	X	X	X	X	X	X	X	X	X
Dispense Artificial Tears/Lubricating Ointment		X	X	X	X	X	X	X	X	X	X	X	X	X	X	X	X
Adverse Events		X	X	X	X	X	X	X	X	X	X	X	X	X	X	X	X

1. Physical exam includes height and weight.

2. Clinical laboratory testing includes chemistry and hematology. Refer to Section 6.7 for more detail.

3. Pregnancy test for all women of childbearing potential. Post randomization (Part 1a) and all WOCBO Part 1b, pregnancy testing only required for intervention treatment group. During the clinical trial, best corrected visual acuity and ocular exams will be performed in both eyes at Visit 1/Screening and Visit 16/Week 24/EOs/ET visits.

4. Best Corrected Visual Acuity and ocular exam will be performed in both eyes at Visit 1/Screening and Visit 16/Week 24/EOs/ET visits. During the clinical trial, best corrected visual acuity and ocular exams will be performed in study eye only.

5. Fundus photographs measured by ultra-wide field imaging. However, standard 4-field or 7-field photos if ultra-wide field imaging is not available. At Screening, fundus photographs not required for subjects with open globe injury and retinal detachment.

6. Post randomization, pregnancy testing required for intervention treatment group.

7. The initial ADX-2191 intravitreal injection may be performed while in the operating room Day 0 or on post-operative Day One.

8. Pre-Injection Assessment by treating investigator to include visual acuity assessment, slit-lamp examination, intraocular pressure measurement, and dilated ophthalmoscopy. Refer to Section 6.13 for more detail. The screening visit should optimally occur within 2 weeks of the Day of Surgery (Visit 2).

9. The screening visit should optimally occur within 2 weeks of the Day of Surgery (Visit 2).

10. If a separate evaluating investigator is not available, the assessment may be made by the treating investigator and noted in the eCRF (section 6.8.4).

11. As of Protocol Version 5.0 (dated May 5 2021), eligible subjects will no longer be randomized and all enrolled subjects will be placed in the Intervention Cohort.

